6.2.6. Feasibility of the measures

- ✓ The number of responses from EORTC-QLQ-C30 and the number of physical activity data are summarized at each measurement point.
- ✓ Time from enrollment to discontinue wearing the device (ie, Time-to-wearable failure) is calculated, and the cumulative rate curve, median, and proportion of time-point continuation are estimated using the Kaplan-Meier method.

CCI

6.4. Subset Analyses

- ✓ Prespecified subset variables for analyses of primary endpoints as follows:
 - Age(59 years of age or younger/ 60 years of age or older),
 - menopausal status (premenopausal/ postmenopausal),
 - PS(0/ 1),
 - line of therapy (first/ second),
 - employment (none or retired/ fulltime or parttime)
 - Education(~ high school diploma or equivalent/ College ~)
 - Visceral metastatic (presence/ absence)
 - Stage (I-III/ IV), (I-II/ III-IV),
 - BMI(18.5 kg/m2 or lower / higher than 18.5 kg/m2)
 - Experience of dose reduction (presence/ absence)
 - Experience of fatigue (presence/ absence)Pre-dose reduction/ post-dose reduction (among patients with dose reductions)

[figure not shown]

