5. MILESTONES

Milestone	Planned date
Start of data collection	01 February 2021
End of patient enrollment	31 August 2022
End of data collection	28 February 2023
Final study report	31 December 2023

PFIZER CONFIDENTIAL

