12.5. Data analysis

For the purpose of this study, analyses will generally be descriptive in nature and will be conducted. All analysis will be summarized separately by groups except for the between group comparison. Detailed methodology for summary and statistical analyses of data collected in this study will be documented in a SAP, which will be dated, filed and maintained by JBCRG and Pfizer. The SAP may modify the plans outlined in the protocol; any major modifications of primary endpoint definitions or their analyses would be reflected in a protocol amendment.

All variables will be summarized descriptively through tabular displays of mean, median, ranges and standard deviations of continuous variables and frequency distributions of categorical variables by measured points.

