1. VERSION HISTORY

Table 1. Summary of Changes

Version/ Date	Associated Protocol Amendment	Rationale	Specific Changes
Version 1.0 (29 Mar 2021)	Amendment 1 (01 Sep 2020)	N/A	N/A
Version 1.1 April 4, 2023			
Detailed the definition of the baseline values [6.1.1.1, 6.1.2.1.]
 
Added the endpoints and secondary analyses; scores of EORTC-QLQ-C30 and physical activity metrics.[3.1., 6.1.1.2., 6.1.2.2.]
 
Added week as the covariate of the mixed-model.[6.1.2.1.]
 
Modify the filter of the physical activity metrics (minutes with “WAKE FILTERED”) [3.1. Physical activity metrics (Sedentary time)]
 
Detailed the definition of the subset analyses [6.4.]
 
add the variables for the subset analyses[6.4.]

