ePRO technologies can provide a new opportunity for routine monitoring to assess patients' condition, because the ability to assess PROs in real-time enables quick clinical decision making and intervention. In addition, application of ePRO might enable better patient clinician communication and lower symptom distress. Also, this kind of ministering provides

a systematically collected symptom data and, thus eventually supports clinical decision making to improve symptom management, which could save a lot of health care provider's time, reduce the number of patients' visits and could enhance adherence.

Wearable devices can objectively measure physical activity. With the rapid development and commercialization in recent years, it has become possible to easily measure patients' physical activity using wearable devices. Gresham et al., 2018 summarized 41 randomized trials using wearable devices conducted on cancer patients between 2005 and 2016, consistent with the trend in recent years that increasing number of clinical trials have examined the relationship between physical activity and clinical outcomes. Some of these studies have suggested that the physical activity of cancer patients correlates with the patient's performance status, quality of life and survival.

To date, there have been few studies in Japan evaluating the day-to-day effects of ABC treatment on patients in a real-world setting, and information about the effects of treatment-induced AEs on patients' daily functioning outside the context of clinical trials is particularly lacking. This study will provide prospective, observational data in the real-world setting to evaluate the impact of ABC treatment and the treatment-related AEs on patients' daily life utilizing novel technologies (ie, ePRO and wearable device).

This statistical analysis plan (SAP) provides the detailed methodology for summary and statistical analyses of the data collected in Study A5481126. This document may modify the plans outlined in the protocol; however, any major modifications of the primary endpoint definition or its analysis will also be reflected in a protocol amendment.

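### SAP v1.1, dated 35 days after the planned end of data collection, calls its added subset variables prespecified and gives both primary endpoints fallback baselines that the protocol does not allow

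*SAP*

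**What the plan says.** **Subsets.** SAP 6.4 places its whole list under one label: "Prespecified subset variables for analyses of primary endpoints as follows". The SAP version history, in the row headed "Version 1.1 April 4, 2023", records that subset definitions were detailed and includes the entry "add the variables for the subset analyses[6.4". Neither place says which variables or cut-points are new.

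**Timing.** Protocol Section 5 plans the end of enrollment for "31 August 2022" and the end of data collection for "28 February 2023".

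**Baselines.** The v1.1 row also records "Detailed the definition of the baseline values" for SAP 6.1.1.1 and 6.1.2.1, the main analyses of the two primary endpoints. Protocol 12.5.1 takes both baselines from measurements made after enrollment and up to the day before treatment. The SAP repeats that rule and adds a fallback to each. A patient with no pre-treatment global health score may use one obtained within 6 days of starting treatment. A patient with fewer than 4 pre-treatment days of activity data uses the first 4 days.

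**Amendments.** Protocol 12.5 says that "any major modifications of primary endpoint definitions or their analyses would be reflected in a protocol amendment", and SAP Section 2 makes the same promise: "any major modifications of the primary endpoint definition or its analysis will also be reflected in a protocol amendment". The protocol's document history ends with Amendment 3 of 20 December 2021, which revised milestone dates. The v1.1 row of the SAP log shows no associated amendment.

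**The concern.** The word prespecified tells a reader that a split was chosen before anyone could know what it would show. For the entries added in v1.1, the documents do not support that assurance. On the planned calendar all the data existed by then, and the entries cannot be told apart from those of v1.0. If the label passes into the tables and the report, late additions will carry the same weight as the original list.

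The baseline matters more for the main result. Both primary endpoints are changes from baseline. If the reference value is taken after treatment has begun, any early effect of treatment on quality of life or activity is partly absorbed into the baseline, and the reported change no longer means what Protocol 12.5.1 says it means. A reader who has only the protocol would not know this.

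**Working it through.** **1. Dates (Protocol Sections 4 and 5; SAP version history).**

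- Planned end of data collection to v1.1: 28 February to 31 March 2023 is 31 days, plus 4 days in April = **35 days**.
- Is the planned end plausible? End of enrollment, 31 August 2022, plus 24 weeks (168 days) = 15 February 2023, which is 13 days before 28 February. The protocol's calendar is consistent.
- Overrun needed for v1.1 to precede the end of collection: 13 + 35 = 48 days. With enrollment ending as planned, the last patient would have to run more than 48 days past 24 weeks.
- Amendment 3 to v1.1: 20 December 2021 to 20 December 2022 is 365 days, plus 105 days to 4 April 2023 = **470 days**.

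**2. Subset list.** SAP 6.4 contains 13 two-way splits: age, menopausal status, performance status, line of therapy, employment, education, visceral metastasis, stage (two cuts), BMI, dose reduction, fatigue, and before versus after dose reduction. The last three appear to rest on events during observation. The number added in v1.1 cannot be recovered, because v1.0 is not among the documents.

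**3. Sedentary-time baseline by number of pre-treatment days, k.** The first 4 days are read here as the first 4 days with measurements.

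| k | Protocol 12.5.1 | SAP 6.1.2.1 main analysis | SAP 6.1.2.1 repeat analysis |
|---|---|---|---|
| 0 | no baseline | 4 days, all from treatment start on | excluded |
| 1 to 3 | mean of the k days | k days before and 4 − k days from treatment start on | excluded |
| 4 or more | mean of the pre-treatment days | same as protocol | same as protocol |

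For k = 3, 2, 1, 0 the share of the baseline taken from treatment start onward is (4 − k)/4 = 25%, 50%, 75%, 100%. If the wording instead means the first 4 days after treatment starts, the share is 100% throughout. Either way, neither SAP analysis reproduces the protocol's. The main analysis mixes in later days, and the repeat analysis drops patients with 1 to 3 pre-treatment days, for whom Protocol 12.5.1, which sets no minimum, gives a valid baseline.

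The early effect can be seen directly. Assume that weeks are counted from treatment start, and take a patient with k = 0 and seven measured days in week 1. Let b be the mean of the first four days (the baseline) and r the mean of the other three. The week-1 change is (4b + 3r)/7 − b = (3/7)(r − b), so four of the seven days are compared with themselves.

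**4. Global health status baseline.** The fallback applies only when nothing was measured before treatment, so every fallback value dates from treatment start or the days just after it. The first scheduled follow-up is Day 15 of Cycle 1 (Protocol Section 6). The SAP plans no analysis without these patients.

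**5. What cannot be computed.** The documents do not give the number of patients who use either fallback, so the shift in the mean change cannot be stated.

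**The case against.** **Whether anyone had seen the data.** A reader might infer that the v1.1 choices were made with outcomes in view. The documents do not show this. The end date is only planned. Protocol Section 10 limits site checks to entry and wearing status, and Protocol 12.2 describes data-manager review for entry and compliance. Protocol 13.4 sends the full data set to the analysis vendor at the end of the study, SAP Section 7 plans no interim analysis, and SAP Section 5 holds the primary analysis until all primary endpoint data are available. On the other side, Protocol 12.2 has regular transfers and sponsor extraction of all data sets, and no blinding is described. Access was possible but is not documented. This part of the objection stands, and it is why the post hoc label should be conditional.

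**Chance findings.** A reader might also count the splits and attach an expected number of false positives. The SAP plans no tests in the subsets. Protocol 12.1 and SAP 5.1 describe a descriptive study without test-based decisions, and the t-tests belong to the association analyses. The harm is mislabelling and selective reporting, not a type I error rate.

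**What counts as major.** The amendment promise covers only major changes. The log also records a changed activity filter and a week covariate in the sedentary-time model. A reader might take these as breaches too, but the protocol names neither a filter nor a mixed model, so they alter no protocol text and there is no case for returning to v1.0 on them. The fallback baselines can be defended as missing-data handling, which Protocol 12.5.4 leaves to the SAP; Protocol Section 10 also only recommends 4 baseline days. That defence is weaker, because the fallback changes the reference point of a change-from-baseline primary endpoint.

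**Disclosure and existing safeguards.** The version history does list the changes by section, but it does not identify the added subset entries. The repeat analysis of sedentary time is a real safeguard, though only a partial one.

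**Conclusion.** The point holds in two parts. First, SAP 6.4 applies the prespecified label to variables that its own log says were added on 4 April 2023, 35 days after the planned end of data collection. Second, both primary endpoints now admit baseline values from treatment start onward, which Protocol 12.5.1 excludes, and the protocol supplied contains no amendment saying so. Sedentary time is partly covered by a sensitivity analysis; global health status is not covered.

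This rests on three assumptions: that collection ended roughly as planned, that the fallbacks are what the log's baseline entry refers to (v1.0 is not available to confirm it), and that moving the reference point of a primary endpoint counts as major. The departure from the protocol's baseline stands whatever the answer to the first two. The documents do not establish that choices were driven by results, and the point does not depend on it. In a descriptive study the consequence is how results are labelled and what the primary change means, so the remedy can be modest.

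**What to change.** 1. In SAP 6.4, mark every subset variable and cut-point as v1.0 (prespecified) or v1.1 (added 4 April 2023, after the planned end of data collection). Label the v1.1 entries post hoc unless it is documented that no outcome data had been seen by that date. Carry the label into the tables and the report, and state the actual end of collection, lock date and data-access status.

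2. Report change in global health status and in sedentary time on the protocol's pre-treatment-only baseline as the primary result, keeping patients with 1 to 3 pre-treatment activity days. Show the fallback-baseline results as a labelled sensitivity analysis, and give the number of patients who use each fallback. Alternatively, issue the protocol amendment that both documents promise and state in it when it was written relative to data collection.

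The v1.1 filter and week covariate can stay.

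Cost: SAP wording and one extra run of the primary tables. Patients without any pre-treatment value leave the primary change analysis, and some subset results may have to be shown as post hoc.

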6. SCHEDULE OF ACTIVITIES

Refer to STUDY PROCEDURES and ASSESSMENTS sections of the protocol for detailed information on each procedure and assessment required for compliance with the protocol.

Procedure / Assessment	Screening	Baseline	Observation period (6 cycles; 24 weeks) ^j		End of Study ^c
			Weekly ^a	Cycle-base ^b	
Time Window			+ 3 days ^d	+ 7 days ^d	
Informed consent	X				
CRF data					
Patient baseline characteristics; Demography, Height, Weight, Medical history, Prior treatment and surgery history, Primary diagnosis, Site of metastatic and disease, Menopausal status, Treatment being initiated, Line of therapy		X			
ECOG performance status ^k		X	↔X↔		X
Adverse event monitoring (eg, type, grade) ^e			↔X↔		
Treatment (eg, type, duration) ^f			↔X↔		
Palbociclib dosing modification ^g			↔X↔		
Concomitant Medication (Surgery, Radiotherapy)			↔X↔		
Disease progression (if applicable)			↔X↔		
Initial treatment discontinuation (if applicable)			↔X↔		
Study withdrawal (if applicable)			↔X↔		
Study completion					X
PRO data via smartphone-based application					
Patient baseline characteristics; Education, Employment		X ⁱ			
EORTC-QLQ-C30		X ⁱ		X	
PRO-CTCAE ^h		X ⁱ	X		
Overall satisfaction with treatment				X	

PFIZER CONFIDENTIAL

Procedure / Assessment	Screening	Baseline	Observation period (6 cycles; 24 weeks) ^j		End of Study ^c
			Weekly ^a	Cycle-base ^b	
Time Window			+ 3 days ^d	+ 7 days ^d	
Physical activity data via wearable device					
Physical activity		X	↔X↔		

- a. Weekly assessment of PRO-CTCAE will be conducted based on Cycle 1 Day 1 regardless of cycle delay.
- b. Cycle-based assessment of EORTC-QLQ-C30 and Treatment satisfaction will be conducted on Day 15 of each cycle.
- c. End of study is defined as end of 6 cycles of initiated treatment. If patients discontinue the initiated treatment before completion of 6 cycles (eg, due to disease progression) and switch to another treatment, end of study will be end of 24 weeks after initiation of initial treatment. In this case, to assess association between change in QOL and physical activity versus disease progression, data collection [including PROs (EORTC-QLQ-C30 and PRO-CTCAE) and physical activity evaluation, EDC data entry] will continue to the end of the study (ie, 24 weeks after the start of the study) even if the treatment is switched to another treatment.

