Another phase 3 study, PALOMA-3, was conducted with HR+/HER2- patients that had relapsed or progressed during prior endocrine therapy. The median PFS was 9.2 months with palbociclib + fulvestrant and 3.8 months with placebo + fulvestrant (hazard ratio=0.42 [95% CI, 0.32-0.56] $P<0.001$). In Japanese subgroup analysis in PALOMA-3, median PFS was 13.6 months in palbociclib + fulvestrant and 11.2 months in placebo + fulvestrant group (hazard ratio= 0.82 [95% CI, 0.32-2.11]). Common AEs with palbociclib + fulvestrant vs placebo + fulvestrant were neutropenia (84.1% vs 3.5%), leukopenia (60.0% vs 5.2%), infections (54.5% vs 34.9%), fatigue (44.1% vs 31.4%), Nausea (35.9% vs 30.8%), Anemia (31.6% vs 14.0%), Stomatitis (30.1% vs 14.0%). Grade 3/4 neutropenia occurred in 69.6% of patients. Among Japanese patients, neutropenia was most common AE in the palbociclib arm (93%) and typically grade 3/4. Accordingly, dose reduction, cycle delays, and dose interruptions were higher in Japanese patients than in the overall populations. In PALOMA-3, EORTC-QLQ-C30 and EORTC-QLQ-BR23 were used to asses PRO. Analysis of PROs between the two treatment groups showed that estimated overall global QOL scores in EORTC-QLQ-C30 significantly favored the palbociclib + fulvestrant (66.1, [95% CI, 64.5-67.7] versus 63.0 [95% CI, 60.6-65.3]; $P=0.0313$). Significantly greater improvement from baseline in pain was also observed in this group (-3.3 [95% CI, -5.1 to -1.5] versus 2.0, [95% CI -0.6 to 4.6]; $p=0.0011$). Also, TTD in global QOL and pain were significantly delayed (hazard ratio=0.64 [95% CI, 0.45-0.91; $p<0.007$, hazard ratio=0.64 [95% CI, 0.49-0.85; $p<0.001$, respectively]).

Cancer treatment is taking place in an outpatient setting. The growing number of oral and subcutaneous medications for oncological diseases lead to new challenges for patients and health care providers. Some of the challenges include continuous patient-physician communication, lack of adherence, potential side effects, which are common and often underreported, and their impact on quality of life (QOL). One of the important purposes of treatment for ABC patients is to improve or maintain QOL, thus, appropriate assessment of patients' QOL and the effect to daily life are important and desirable to making appropriate treatment decisions and assisting in timely delivery of care.

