Patients will complete PRO assessment in weekly, and cycle-basis and wear the wearable device for 6 cycles. At the patients' regular clinical visits at approximately 30 day interval, they will bring the device worn in the past period, and study site staff will confirm if the returned wearable device is still functional and upload the physical activity data through Actigraph application (ie, ActiSync) into the Actigraph cloud system (ie, Actigraph CentrePoint). Detailed information will be included in User Manual and training for Actigraph CentrePoint for the sites. For the PRO and physical activity data collected from the patient, the data entry status or wearing status will be confirmed, but the data itself will not be confirmed. In addition, investigators or study site staff will complete eCRF to capture treatment changes and clinical outcomes (eg, adverse event) for 6 cycles after enrollment listed in SCHEDULE OF ACTIVITIES.

If a patient has not entered any data through ePRO application for 4 consecutive weeks or if a patient has not worn the wearable device for 4 consecutive weeks, the study site staff will be notified and asked to reach out to the patient.

Even if patients discontinue the initiated treatment before completion of 6 cycles and switch to another treatment, to assess association between change in QoL and physical activity versus disease progression, data collection (including PROs [EORTC-QLQ-C30 and PRO-CTCAE] and physical activity evaluation, EDC data entry) will continue to the end of the study (ie, 24 weeks after initiation of initial treatment).

End of Study

End of study is defined as end of 6 cycles of initiated treatment. If patients discontinue the initiated treatment before completion of 6 cycles (eg, due to disease progression) and switch to another treatment, end of study will be end of 24 weeks after initiation of initial treatment.

Investigators or study site staff will complete CRF to capture End of Study information listed in Section 6 SCHEDULE OF ACTIVITIES.

Patients will return the wearable device to study site staff. Study site staff will stop the collection of the physical activity data via configuration in Actigraph system (ie, Actigraph CentrePoint). Detailed information will be included in User Manual and training for Actigraph CentrePoint for the sites.

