3. ENDPOINTS AND BASELINE VARIABLES: DEFINITIONS AND CONVENTIONS

3.1. Primary Endpoint(s)

- *EORTC-QLQ-C30 (Global health status scale)*
 - The EORTC-QLQ-C30 is a 30-item questionnaire to evaluate cancer patients' QOL, and it's composed of five multi-item functional subscales (physical, role, emotional, cognitive, and social functioning), three multi-item symptom scales (fatigue, nausea/vomiting, and pain), a global quality of life (QOL) subscale, and six single item symptom scales assessing other cancer-related symptoms (dyspnea, sleep disturbance, appetite loss, constipation, diarrhea, and the financial impact of cancer). The questionnaire employs 28 4-point Likert scales with responses from "not at all" to "very much" and two 7-point Likert scales for global health and overall QOL. Responses to all items are then converted to a 0 to 100 scale. For functional and global QOL scales, higher scores represent a better level of functioning/QOL. For symptom-oriented scales, a higher score represents more severe symptoms. A 10-point or higher change in scores from baseline is considered clinically significant.
 - Change of scores from baseline at each cycle
 - Scores at each cycle
- *Physical activity metrics (Sedentary time)*

All the physical activity metrics variables will be analyzed with "WEARFILTERED" (ie. "Wear" = TRUE.)

- Average of a week, which includes 5 or more days of wearing 10 hours or longer during a day except for bedtime.
- Change from baseline at each week
- Sedentary time (sedentary time means) at each week

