6.5.3. Study Treatment Exposure

The extent of treatment will be summarized as follows:

- Number of cycles started
- Duration of a cycle (weeks)

For Group 1 (palbociclib plus endocrine therapy)

- Starting dose: 125 mg, 100 mg, 75 mg
- Number of patients with no dose reduction, at least 1 dose reduction, 2 dose reductions
- Patients with cycle delay

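### SAP 6.4 splits the primary endpoints by events that occur during follow-up (dose reduction, probably fatigue) as if they were baseline traits, so the contrasts can show differences when the event has no effect

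*SAP*

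**What the plan says.** SAP 6.4 opens its list with "Prespecified subset variables for analyses of primary endpoints as follows". Most entries are fixed at baseline: age, menopausal status, performance status, line of therapy, employment, education, visceral metastasis, stage and BMI. Three are not, or probably not:

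- "Experience of dose reduction (presence/ absence";
- experience of fatigue, present or absent, with no source or time window;
- "Pre-dose reduction/ post-dose reduction (among patients with dose reductions".

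The legible text of 6.4 gives no event window, landmark, time-dependent handling or caveat for these three. A figure follows the list and could not be read.

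Other sections bear on the point:

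- SAP 6.1.1.1 and 6.1.2.1 report change in global health status at each measurement point and change in sedentary time by week. Each adds a repeated-measures mixed model with group, cycle and their interaction.
- SAP 6.5.3 counts dose reduction over treatment exposure, for Group 1 only: "Number of patients with no dose reduction, at least 1 dose reduction, 2 dose reductions".
- Protocol 10 says that, after a patient stops the initial treatment and switches, "data collection (including PROs [EORTC-QLQ-C30 and PRO-CTCAE] and physical activity evaluation, EDC data entry) will continue to the end of the study", that is, to week 24.

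**The concern.** A subset fixed at baseline describes the same kind of patient at every time point. An ever/never subset does not. A patient first reduced in Cycle 5 is already placed among the reduced in the Cycle 1 row.

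For dose reduction, time at risk is also unequal. A patient who progresses early and stops palbociclib can no longer be reduced, so she tends to stay in the no-reduction subset. Her later scores still count there.

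The pre/post split compares earlier with later cycles within a patient. Any time trend enters the contrast unless cycle is adjusted for. If reductions follow temporarily low scores, regression to the mean enters too.

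At stake is interpretation. The study sets out to evaluate how treatment and its adverse events affect daily life, so readers will take these contrasts as effects of reduction or fatigue.

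**Working it through.** The plan gives no figure to reproduce: Protocol 12.1 sets the sample size on a practical basis. The checks below give the event no effect at all. Event rates, SDs and the fall after progression are assumptions.

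**1. Future information.** With a constant rate *h* per cycle over six cycles and everyone at risk throughout, the share of the ever-reduced not yet reduced by the end of cycle *c* is 1 − [1 − (1−h)^c] / [1 − (1−h)^6]. For h = 0.10 the denominator is 1 − 0.9^6 = 0.4686. Cycle 1 gives 1 − 0.100/0.4686 = 0.79, and Cycle 3 gives 1 − 0.271/0.4686 = 0.42.

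| h | Ever reduced | Not yet, Cycle 1 | Not yet, Cycle 3 |
|---|---|---|---|
| 5% | 26% | 81% | 46% |
| 10% | 47% | 79% | 42% |
| 20% | 74% | 73% | 34% |

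These shares show misclassification. They do not by themselves create a difference.

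**2. Unequal time at risk.** Take the median PFS values in Protocol 7 (24.8, 13.6 and 9.2 months). The chance of progression per 28-day cycle is 1 − 0.5^[(28/30.44)/median], which gives 0.025, 0.046 and 0.067. Assume that progression ends palbociclib and is followed by a lasting fall of 10 to 15 points. With h = 0.10 and progression pre-empting reduction in the same cycle:

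| Median PFS (months) | Progressed by Cycle 6, never reduced | Progressed by Cycle 6, ever reduced | Spurious advantage of ever reduced (10- and 15-point fall) |
|---|---|---|---|
| 24.8 | 19.8% | 7.0% | 1.3 and 1.9 |
| 13.6 | 32.6% | 12.6% | 2.0 and 3.0 |
| 9.2 | 43.6% | 18.2% | 2.5 and 3.8 |

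For example, (0.436 − 0.182) × 15 = 3.8. Over h = 5% to 20% the range is 1.0 to 5.4. If reduction may also occur in the cycle of progression, the range at h = 10% is 0.9 to 2.6.

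**3. Other mechanisms.** Simulation used 1,500 replicates, 80 patients, six cycles, between-patient SD 15, within-patient SD 14 and a base reduction rate of 10% per cycle. Ever/never compares patient means; pre/post is within reduced patients.

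| Scenario | Ever minus never | Post minus pre |
|---|---|---|
| Event unrelated to score, no dropout, no trend | 0.0 | 0.1 |
| Random reduction; poorer patients drop out, base rate 5–8% per cycle | +1.1 to +3.9 | about 0 |
| Shared patient-level cause, correlation 0.2 / 0.3 / 0.5 | −3.0 / −4.5 / −7.5 | about 0 |
| Early 6-point dip that recovers | about 0 | +3.6 |
| Decline of 1 point per cycle | about 0 | −3.0 |
| Reduction more likely after a temporary low score | −1.4 to −2.9 | +2.6 to +4.7 |

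**4. Fatigue.** The bias depends on the undefined source. Protocol 16.2.4.2 stops non-serious AE recording when new therapy starts, so an AE-based label has a shorter window after a switch. PRO-CTCAE is answered weekly: "Weekly assessment of PRO-CTCAE will be conducted based on Cycle 1 Day 1 regardless of cycle delay". With chance *p* per response, P(ever) = 1 − (1−p)^k. At p = 5% this is 18.5% for k = 4 responses and 70.8% for k = 24, so the label partly measures how many forms were answered. Fatigue is also a scale of the outcome questionnaire, among "three multi-item symptom scales (fatigue, nausea/vomiting, and pain", so a shared cause is plausible.

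**5. Landmark.** With status fixed at the end of Cycle 2 and scores taken from Cycle 3, the dropout artefact falls to 0.0. The shared-cause artefact barely moves: −4.5 becomes −4.0, and −7.5 becomes −7.0. Numbers are small. With 20 to 80 patients, 10% is 2 to 8 reduced by the end of Cycle 1, and 1 − 0.9² = 19% is about 4 to 15 by the end of Cycle 2.

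**The case against.** The study is descriptive. SAP 5.1 plans no decision from tests, and Protocol 14 calls the work hypothesis-generating and cautions on causality. Section 6.4 is supplementary. The AE objective is served by SAP 6.2.1 and 6.2.2, which classify patients with and without an AE or symptom at each cycle. All this stands and limits the severity. It does not cure a Cycle 1 row for reduced patients most of whom have not been reduced.

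A reader might infer more than the documents support:

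- *That the splits must produce differences.* They need not: the control scenario gives essentially zero.
- *That reduced patients will look better.* A shared cause reverses the sign, and the gains in step 2 rest on an assumed fall after progression.
- *That pre/post would rise by 5 to 8 points with no effect.* That requires reduction to follow a score at least one within-patient SD low. The documents state no such trigger. Protocol 7 describes neutropenia in Japanese patients and continues: "Accordingly, dose reduction, cycle delays, and dose interruptions were higher in Japanese patients than in the overall populations".
- *That pre/post has no control for time.* This is not established. The list is for analyses of the primary endpoints, and their mixed model contains cycle; 6.4 does not say whether pre/post runs within it.
- *That the time-at-risk argument for palbociclib covers fatigue.* It does not: PRO-CTCAE continues after a switch. Since PRO-CTCAE also has a baseline assessment, ever during follow-up is the likely reading of the fatigue variable, not a stated one.

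**Conclusion.** The concern holds in limited form. Ever/never dose reduction, and fatigue if it means ever during follow-up, are follow-up events used to sort results that precede them. For dose reduction, time at risk is also unequal. The 79% and 42% shares are exact given a constant 10% rate per cycle, which is an assumption; the shares for 5% and 20% lead to the same conclusion.

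Spurious differences can arise, but their sign and size cannot be derived from the documents. Under assumed inputs they run from about +1 to +5 points (timing or dropout) and from −3 to −7.5 (shared cause). All lie below the 10-point change that SAP 3.1 treats as clinically significant, though the larger ones are not negligible beside it. The pre/post contrast is open to time trend unless it is run in the model with cycle, and to regression to the mean if reductions follow temporarily low scores.

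Severity is minor to moderate: no primary result depends on 6.4.

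**What to change.** - Move dose reduction, fatigue and pre/post out of the baseline subset list into a separate paragraph of SAP 6.4.
- Define each event, its source and its window. For fatigue, state whether it is the investigator-reported AE or PRO-CTCAE, with the threshold and whether baseline symptoms count.
- Replace ever/never and pre/post with one time-varying indicator per event: the event has occurred before this assessment. Add it to the existing mixed model with cycle. For dose reduction, use Group 1 only and limit the analysis to time on the initiated treatment.
- Label the results as descriptive, non-causal associations.
- Keep an early landmark only as a sensitivity analysis, given the small numbers in step 5.

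The cost is SAP wording and slightly more programming; AE and dosing data are already collected throughout observation. Precision is lower, and time after a switch is left out of the dose-reduction analysis. Confounding remains. Regression to the mean can also remain, because a low score that prompts a reduction still falls on the before side. The time-varying form was not simulated.
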